4.3. Justification for Dose

This study will assess 40 mg of GB001 in adult subjects with chronic rhinosinusitis with or without bilateral nasal polyps. In a previous asthma study (PTR-36-201), GB001 5 mg and 20 mg doses were evaluated. While both doses of GB001 were effective compared to placebo in decreasing the proportion of subjects with asthma worsening/exacerbations in a treatment withdrawal design, the 20 mg dose produced a larger treatment effect (20 mg: 20.8%; 5 mg: 32.7%; placebo: 52.8%). In addition, only the 20 mg dose demonstrated statistical significance for the endpoints of asthma control, Asthma Control Questionnaire (ACQ-5), and time to asthma worsening relative to placebo. However, no improvements in lung function were observed, suggesting that higher doses are needed to achieve clinical benefit across different endpoints, including lung function. A comparable safety profile was observed across all treatment arms (including placebo) in this study. Considering that patients with chronic rhinosinusitis with eosinophilic inflammation manifest with more inflammation and disease severity than patients with asthma in general, a dose of 40 mg should be adequate and safe to investigate the efficacy and safety of GB001 in this patient population. The selection of this dose encompasses the totality of PK, efficacy, and safety data of GB001 available to date.

4.4. End of Study Definition

Subjects will be regarded to have completed the study if he/she completes the Week 16 visit. The end of the study is defined as the date of the last visit of the last subject in the study.

5. STUDY POPULATION

Prospective approval of protocol deviations to recruitment and enrollment criteria, also known as a protocol waiver or exemption, is not permitted.

5.1. Inclusion Criteria

Prior to randomizing a subject, additional randomization criteria in [Section 5.3](#) must be met.

Subjects are eligible to enter the Run-in period only if all of the following criteria are met:

1. **Informed Consent:** Capable of giving signed informed consent which includes compliance with the requirements and restrictions listed in the informed consent form (ICF) and in this protocol.
2. **Age:** ≥ 18 to 75 years of age at the time of Screening visit.
3. **Sex:** Males or females:
 - a. Women of childbearing potential (WOCBP) must use an acceptable method of contraception (see Appendix 4, [Section 10.4](#)) at least 1 month prior to screening through 28 days after the last dose of IP.
4. **Diagnosis:** Diagnosis of chronic rhinosinusitis with or without bilateral nasal polyps for at least 12 weeks prior to Visit 1.
5. **Nasal symptoms:** Presence of at least two of the following symptoms prior to Visit 1:
 - nasal blockade/obstruction/congestion
 - nasal discharge (anterior/posterior nasal drip)
 - facial pain/pressure
 - reduction or loss of smell
6. **INCS:** Subjects must be on a stable administration of intranasal corticosteroids (INCS) for ≥ 2 months prior to Visit 1. For subjects using a specialized delivery device (eg, XHANCE™) or corticosteroids administered via irrigation (eg, budesonide + sterile saline), they must be on MFNS for ≥ 2 weeks prior to screening.

5.2. Exclusion Criteria

Subjects are excluded from the study if any of the following criteria apply:

1. **Nasal symptoms:** SNOT-22 score < 20 as assessed at screening.
2. **Prior polyp surgery:** Subjects who have undergone any nasal surgery (excluding polypectomy performed as an outpatient procedure) within 4 months before screening or have had ≥ 4 sinonasal surgeries in the past.
3. **Comorbidities:** Presence of a known pre-existing clinically important condition including: active tuberculosis, pulmonary fibrosis, bronchopulmonary aspergillosis, eosinophilic granulomatous polyangiitis (Churg-Strauss syndrome), Young's syndrome, Kartagener's syndrome or dyskinetic ciliary syndromes, and cystic fibrosis. Clinically significant endocrine, autoimmune, metabolic, neurological, renal (calculated creatinine

clearance < 60 mL/min), gastrointestinal, hepatic, cardiovascular, hematological, or any other system abnormalities that are uncontrolled with standard treatment.

4. **Malignancy:** A current malignancy or previous history of cancer in remission for less than 5 years prior to screening (subjects will not be excluded if they had localized carcinoma of the skin that was resected for cure).
5. **Liver Disease:** Known pre-existing liver disorders (ie, non-alcoholic fatty liver disease (NALFD) or Gilbert's syndrome), or unstable liver disease (as defined by the presence of ascites, encephalopathy, coagulopathy, hypoalbuminemia, esophageal or gastric varices or persistent jaundice), cirrhosis, or known biliary abnormalities.
6. **Prior anti-inflammatory treatment:** Subjects who have required a burst of systemic corticosteroids (eg, oral, intravenous, intramuscular corticosteroids) within the 1 month before screening or are scheduled to receive systemic corticosteroids during the study period for another condition, or who have required intranasal corticosteroid drops within 1 month prior to screening.
7. **Intolerant to mometasone furoate nasal spray.**
8. **Specific conditions/concomitant diseases:** Subjects with conditions such as: antrochoanal polyps, nasal septal deviation that would occlude at least one nostril; acute sinusitis, invasive fungal rhinosinusitis, neutrophilic polyposis, nasal infection or upper respiratory infection at screening or in the 2 weeks before screening. Subjects requiring chronic systemic antibiotic treatment for rhinosinusitis.
9. **Ongoing rhinitis medicamentosa.**
10. **ECG Assessment:** Subjects with QTcF \geq 450 msec for males or QTcF \geq 470 msec for females on the Screening visit ECG. However, if QTcF is above this prespecified limit and there are no other clinically significant ECG abnormalities in the opinion of the Investigator, the assessment can be repeated in triplicate. The triplicate QTcF values should be averaged by the Investigator to determine eligibility of the subject to enter the Run-in period. However, if any of the triplicate ECGs show a clinically significant abnormality in the opinion of the Investigator, the subject should be excluded, regardless of the average QTcF of the triplicates.
11. **Alcohol/Marijuana/Illlicit Drugs/Substance Abuse:** A known or suspected history of alcohol misuse, marijuana, illicit drugs, or substance abuse within 12 months prior to Screening visit.
12. **Smoking history:** Asthma or COPD patients that are current smokers (any substance), or former smokers with a smoking history of \geq 10 pack-years [(number of cigarettes per day/20) \times number of years smoked]. A former smoker is defined as a subject who quit smoking at least 6 months prior to Screening visit. This includes electronic cigarettes and vaping.
13. **Immunodeficiency:** A known immunodeficiency, including that due to human immunodeficiency virus (HIV), other than that explained by systemic corticosteroid use.
14. **Investigational medications:** Subjects who have received treatment with an investigational medication within the past 30 days or within 5 half-lives of the

medication, whichever is longer, prior to Screening visit (this also includes investigational formulations of marketed products).

- 15. Receiving prohibited medications:** Refer to Appendix 10 ([Section 10.10](#)) for more details.
 - a. Regular use of systemic corticosteroids or immunosuppressive therapies including methotrexate or azathioprine
 - b. Monoclonal antibodies used in the treatment of asthma
 - c. Medications, food or drink that are moderate or strong CYP3A4 inhibitors or inducers
 - d. Other medications that have the potential for interaction with GB001
 - e. Medications that have a black-box warning for hepatic toxicity.
- 16. Prior participation in a study with GB001:** Subjects who previously participated in a study with GB001 (also named PTR-36 or ADC3680).
- 17. Hypersensitivity:** A known sensitivity to GB001 or any of its excipients. Subjects with rare hereditary problems of galactose intolerance, the Lapp lactase deficiency, or glucose-galactose malabsorption. Subjects with mild-moderate lactose intolerance are not excluded. Subjects with sensitivity or intolerance to aspirin (ie, subjects with aspirin-exacerbated respiratory disease [AERD] with or without desensitization).
- 18. Pregnancy:** Subjects who are pregnant or breastfeeding. Subjects should not be enrolled if they are planning to become pregnant during the time of study participation. A serum pregnancy test is required of all females of child-bearing potential at Screening.
- 19. Adherence:** Subjects who have a known lack of adherence to medications such as INCS.
- 20. Body Mass Index (BMI):** BMI is $\geq 40 \text{ kg/m}^2$.
- 21. Participation:** Subject has any other condition or reason that, in the opinion of the Investigator, would prohibit the subject from participating in the study.
- 22. Participation in another clinical study:** Subjects currently participating in an interventional clinical study with a biologic agent or who have received study drug in another clinical study are not to be considered for participation until the completion of the safety follow-up visit or following a non-investigational drug period of no less than five half-lives. Subjects may not participate in another interventional clinical trial while enrolled in this study.

5.3. Randomization Criteria

Subjects must fulfill the following criteria to be randomized to study treatment:

1. **Diary compliance:** Compliance with completion of the Diary as defined as:
 - a. Completion of questions on 4 or more of the last 7 days immediately prior to Visit 2 (includes the morning of Visit 2).
 - b. **Note:** If the Diary was completed on < 4 days due to technical challenges, the Visit 2 may be delayed up to an additional 3 days to allow for completion of the Diary parameters above.
2. **Eosinophilic Phenotype:** Subjects must meet at least one of the criteria below.
 - Blood eosinophil count ≥ 250 cells/ μ L obtained at Visit 1.
OR
 - Minimum NPS of 4 out of a maximum score of 8 with a score of at least 2 for each nostril as assessed by a blinded central reader. Subjects with an NPS of 1-3 are not eligible for randomization.
3. **CRS exacerbation:** Subjects who experience a CRS exacerbation during the Run-in period should have their Randomization Visit (Visit 2) delayed until the investigator considers the subject has returned to their baseline status. If a 4-week Run-in period has elapsed before the subject is back to baseline status, then the subject will be considered a Run-in failure. CRS exacerbation is defined in [Section 8.1.6](#).
4. **Laboratory abnormality:** No evidence of clinically significant abnormality in the hematological, biochemical, or urinalysis at Screening visit, as judged by the investigator.
5. **Hepatitis status:** No diagnosis of chronic hepatitis B or C, as evidenced by a negative hepatitis B surface antigen (HBsAg) or hepatitis C antibody screen at Screening visit.
6. **Chemistry and hematology obtained at Screening visit:**
 - ALT $\leq 1 \times$ the upper limit of normal (ULN)
 - AST $\leq 1 \times$ ULN
 - Alkaline phosphatase $< 2 \times$ ULN
 - Bilirubin $< 1 \times$ ULN
 - Absolute eosinophil count $< 1,500$ cells/ μ L
 - White blood cell count $< 15,000$ cells/ μ L
7. **Pregnancy test:** For WOCBP, both the serum pregnancy test at the Screening visit and the urine pregnancy test at Visit 2 must be negative.
8. **Use of MFNS:** Subject newly switched onto MFNS during screening should tolerate MFNS during Run-in.
9. **Nasal symptoms:** SNOT-22 score ≥ 17 as assessed at randomization.
10. **ECG overread:** ECG overread by the central ECG reader confirms the QTcF interval is < 450 msec for males or QTcF < 470 msec for females.

5.4. Screen or Run-In Failures

Subjects will be assigned a subject number at the time of signing the ICF and entry into the online registration system (IRT). Subjects who do not enter the Run-in period will be labeled as screen failures.

Subjects who enter the Run-in period but are not randomized will be designated as Run-in failures, even if they complete the Run-in period.

A minimal set of Screen failure/Run-in failure information is required to ensure transparent reporting of Screen/Run-in failure subjects to meet the Consolidated Standards of Reporting Trials (CONSORT) publishing requirements and to respond to queries from regulatory authorities. Minimal information includes demography, Screen/Run-in failure details, eligibility criteria, and any serious adverse event (SAE).

Subjects who are not randomized may be eligible to rescreen upon approval by the Sponsor and/or designated Medical Monitor. A new subject number will be assigned if approved to rescreen. One rescreen is permitted.

6. INVESTIGATIONAL PRODUCT

6.1. Investigational Product Administered

Table 1: Investigational Product Formulation by Treatment Group

Treatment Groups	GB001 40 mg	Placebo
Dose Formulation	20 mg Film-Coated Tablet	
Unit Dose Strength(s)	2 × 20 mg tablet	
Dosage Level(s)	40 mg	
Route of Administration and Instructions	Oral, in the morning on an empty stomach ^a	
Packaging and Labeling	GB001 and placebo film-coated tablets will be packaged in a blinded manner in high-density polyethylene (HDPE) 50 mL bottles. The bottles will be labeled as required per country requirement.	
Storage Requirements	IP should be stored at room temperature (20–25°C) in the original packaging. Protect from moisture. IP stored at site will be maintained under controlled, temperature monitored conditions. Excursions between 15–30°C are permitted. Any other excursion from the required storage condition will be reported to the Sponsor as soon as practical.	

^a No food intake. Liquids are acceptable.

6.2. Preparation/Handling/Storage/Accountability

1. The investigator or designee must confirm appropriate temperature conditions have been maintained during transit for all IP received and any discrepancies are reported and resolved before use of the IP.
2. Only subjects enrolled in the study may receive IP and only authorized site staff may supply IP. All IP must be stored in a secure, environmentally controlled, and monitored (manual or automated) area in accordance with the labeled storage conditions with access limited to the investigator and authorized site staff.
3. The investigator, institution, or the head of the medical institution (where applicable) is responsible for IP accountability, reconciliation, and record maintenance (ie, receipt, reconciliation, and final disposition records).
4. Further guidance and information for the final disposition of IP are provided in the Pharmacy Manual.

6.3. Randomization and Blinding

6.3.1. Randomization

All subjects will be centrally randomized to IP treatment group using an Interactive Response Technology (IRT). Before the study is initiated, directions for use of the system will be provided to the sites.

Randomization will be stratified by country, the presence or absence of NP (CRSwNP and CRSsNP), and the presence or absence of comorbid asthma among CRSwNP subjects. Presence of NP is defined by a minimum NPS of 4 out of a maximum score of 8 with a score of at least 2 for each nostril. Absence of NP is defined as an absence of NP based on visual examination or an NPS of 0 based on nasal endoscopy. Presence of comorbid asthma is defined as a diagnosis of asthma by a physician according to Global Initiative for Asthma (GINA) guidelines at screening or prior to study entry. The CRSwNP stratum will consist of approximately 64 subjects, and the CRSsNP stratum will consist of approximately 36 subjects.

6.3.2. Assignment of Investigational Product Bottle Numbers

IP will be dispensed at the study visits as summarized in SoA. At the Randomization Visit, the IRT system will assign an IP bottle number based on the subject's randomized treatment group.

For subsequent visits when IP is dispensed, the IRT system will assign new IP bottle numbers based on the subject's randomized treatment group.

6.3.3. Unblinding of an Individual Subject

The IRT system will be programmed with blind-breaking instructions. In case of a medical emergency, the investigator has the sole responsibility for determining if unblinding of a subject's treatment assignment is warranted. Subject safety must always be the first consideration in making such a determination. If the investigator decides that unblinding is warranted, the investigator, when possible, should make an effort to contact the Sponsor to discuss unblinding a subject's treatment assignment, unless this could delay emergency medical

treatment of the subject. If a subject's treatment assignment is unblinded, the Sponsor must be notified within 24 hours after breaking the blind. The date and reason that the blind was broken must be recorded in the source documentation and electronic case report form (eCRF).

Appropriate personnel at the Sponsor will unblind suspected unexpected serious adverse reactions (SUSARs) for the purpose of regulatory reporting. The Sponsor will submit SUSARs to Regulatory Agencies in blinded or unblinded fashion according to local law. The Sponsor will submit SUSARs to Investigators in a blinded fashion.

Designated Sponsor (or designee) personnel will have access to unblinded individual subject treatment assignments for the purposes of study-required activities including management of IP inventory and performance of bioanalytical analysis of PK concentrations.

Up to 3 Sponsor individuals not directly involved in the conduct of the study may access unblinded individual subject treatment assignments during the course of the study for the purpose of performing informal analyses to inform further development of GB001. No modifications will be made to the study based on this unblinded access, and there will be no communication of any analyses performed or their results outside of these designated Sponsor individuals. Subjects, investigators and other site personnel, and Sponsor (or designee) personnel who are directly involved in the conduct of the study will remain blinded to treatment assignments until after the completion of the study and the database has been locked.

6.4. Investigational Product Compliance

For additional details refer to Study Reference Manual and/or Pharmacy Manual.

IP accountability will be assessed at each visit by counting returned tablets. Deviation(s) from the prescribed dosage regimen will be evaluated per guidelines provided in the Study Reference Manual and the Pharmacy Manual. Subjects who demonstrate poor IP compliance, in the opinion of the Investigator, should be reeducated on the importance of taking their medications.

Guidance for Missed Dose(s)

If a dose is missed, subjects should be instructed to skip the missed dose and resume dosing at their next scheduled dosing time. For additional details refer to Study Reference Manual and Pharmacy Manual.

6.5. Concomitant Therapy

Subjects should remain on their stable dosing treatment (mometasone furoate [eg, NASONEX® or a generic such as other mometasone furoate nasal sprays (eg, as available from Apotex Corp, Amneal Pharmaceuticals, LLC, Sandoz Inc)] 50 micrograms/actuation Nasal Spray) for the duration of their time on study. If a subject discontinues from IP or withdraws from the study due to lack of efficacy, SOC therapy should not be adjusted until after the Safety Follow-up visit.

Any medication or vaccine (including over-the-counter or prescription medicines, vitamins, and/or herbal supplements) that the subject is receiving at the time of enrollment or receives during the study must be recorded along with:

- Reason for use
- Dates of administration including start and end dates
- Dosage information including dose and frequency

The Medical Monitor should be contacted if there are any questions regarding concomitant or prior therapy.

6.5.1. Prohibited and Restricted Medications Prior to the Screening Visit and Throughout the Study

Please refer to Appendix 10 ([Section 10.10](#)) for prohibited and restricted medications and other treatments.

6.6. Dose Modification

Dose modifications of IP are not permitted. Subjects who are unable to tolerate their assigned dose of IP must be discontinued from IP.

6.7. Intervention After the End of the Study

There is no plan for intervention following the end of the study.

7. DISCONTINUATION OF INVESTIGATIONAL PRODUCT AND SUBJECT DISCONTINUATION/WITHDRAWAL

7.1. Discontinuation of Investigational Product

Permanent discontinuation of IP does not mean withdrawal from the study, and the subject will be encouraged to remain in the study and continue to complete all study visits and diaries as per the SoA ([Section 1.3](#)). If a subject permanently discontinues IP prior to Visit 6 (Week 12) and remains in the study through Visit 7 (Week 16), the subject will not need to return for the Follow-up Visit (Week 20) as the Week 16 Visit will serve as an acceptable Follow-up visit.

Mandatory criteria for permanent discontinuation of IP are documented in Appendix 6 [Section 10.6](#). A subject must permanently discontinue IP if the subject experiences a drug-induced liver disorder.

For subjects who simultaneously discontinue IP and withdraw early from the study, the EW Visit procedures should be conducted ([Section 1.3](#)), and a separate Early Discontinuation of IP Visit is not needed. The subjects should be encouraged to return for the Follow-up Visit.

7.1.1. Pregnancy

A subject must permanently discontinue IP if the subject becomes pregnant. See Appendix 4 [Section 10.4](#) and [Section 8.3.5](#) for additional details.

The Early Discontinuation of IP Visit procedures should be conducted, as shown in the SoA ([Section 1.3](#)), and a separate Early Withdrawal from Study Visit is not needed.

7.1.2. Liver Safety

A subject must permanently discontinue IP if the subject meets the liver chemistry criteria that are specified in Appendix 6 [Section 10.6](#).

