10.6. Appendix 6: Liver Safety - Actions and Follow-up Assessments

Liver chemistry will be evaluated as specified in the SoA ([Section 1.3](#)) and Appendix 2 ([Section 10.2](#)). Parameters will include ALT, AST, GGT, bilirubin, total bile acids, and ALP.

For subjects with ALT or AST $> 1 \times \text{ULN}$ and $< 3 \times \text{ULN}$ or total bilirubin or direct bilirubin $> 1 \times \text{ULN}$ and $\leq 1.5 \times \text{ULN}$, confirm the value within 24 to 48 hours. Contact the Medical Monitor to determine the appropriate liver monitoring schedule (eg, weekly or twice a week).

The criteria requiring additional liver monitoring with possible interruption of study intervention are detailed in [Table 5](#).

Table 5: Liver Chemistry Criteria Requiring Additional Monitoring with Possible Interruption of Investigational Product

Criterion	Actions
ALT or AST $\geq 3 \times \text{ULN}$ and $< 5 \times \text{ULN}$ or total bilirubin or direct bilirubin $> 1.5 \times \text{ULN}$ without symptoms believed to be related to liver injury or hypersensitivity, and who can be monitored weekly for 4 weeks	
Notify the Medical Monitor within 24 hours of learning of the abnormality to discuss subject safety. “Additional Liver Panel” in Table 6 may be requested by the Medical MonitorConfirm values within 24 to 48 hours via repeat labs. If unable to obtain repeat labs within 48 hours, discontinue IP.Decision to continue or interrupt study intervention will be determined by the Investigator and the Medical MonitorSubject must return weekly or more frequently for repeat liver chemistry tests (ALT, AST, GGT, ALP, total bile acids, and bilirubin) until the abnormalities resolve, stabilize, or return to baseline.If at any time the subject meets liver chemistry interruption criteria (as specified in Table 6), then follow the instructions in “Actions and Follow-up Assessments” in Table 6 and in consultation with the Medical Monitor initiate relevant assessment procedures.

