In the case of AEs of interest ([Section 10.3.3](#)), potential re-challenge will be restricted to potential DILI cases that have been assessed as unlikely or not related to IP by the HAC and after liver enzymes have returned to baseline levels. When re-challenging with IP, obtain repeat liver chemistries twice weekly in the first 2 weeks and then weekly for 6 weeks after the re-challenge. If there is a rise in liver enzymes $> 2 \times \text{ULN}$, the IP should be discontinued permanently.

The criteria requiring interruption of IP with additional liver monitoring is detailed in [Table 6](#).

Table 6: Liver Chemistry Criteria Requiring Investigational Product Interruption and Additional Monitoring

Liver Chemistry – IP Interruption Criteria	
ALT/AST (single occurrence)	ALT or AST $\geq 5 \times$ ULN
ALT/AST	ALT or AST $\geq 3 \times$ ULN persists for ≥ 4 weeks
+ Bilirubin ^{a,b}	ALT or AST $\geq 3 \times$ ULN and bilirubin $> 2 \times$ ULN ($> 35\%$ direct bilirubin)
+ INR ^b	ALT or AST $\geq 3 \times$ ULN and international normalized ratio (INR) > 1.5 , if INR measured
+ Cannot Monitor	ALT or AST $\geq 3 \times$ ULN and cannot be monitored weekly for 4 weeks
+ Symptomatic ^c	ALT or AST $\geq 3 \times$ ULN associated with symptoms (new or worsening) believed to be related to liver injury or hypersensitivity
Actions and Follow-up Assessments	
Actions	Follow-Up Assessments

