
 Immediately discontinue IP Report the event to the Medical Monitor within 24 hours Complete the liver event eCRF and complete an SAE data collection tool if the event also met the criteria for an SAE^b Perform liver chemistry follow-up assessments. Monitor the subject until liver chemistry test abnormalities resolve, stabilize, or return to baseline (see MONITORING) Do not restart/rechallenge subject with IP unless Medical Monitor approval is granted If restart/rechallenge not granted, permanently discontinue IP and continue subject in the study for any protocol specified follow up assessments 
MONITORING:
 
 Repeat liver chemistry tests (include ALT, AST, GGT, alkaline phosphatase, total bile acids, bilirubin, and INR) and perform liver event follow-up assessments within 24 hours Monitor subject twice weekly until liver chemistry test abnormalities resolve, stabilize, or return to baseline A specialist or hepatology consultation is recommended 	
Additional Liver Panel
 
 Viral hepatitis serology ^d Obtain INR and recheck with each liver chemistry assessment until the ALT and/or AST values show downward trend Obtain blood sample for pharmacokinetic (PK) analysis Serum creatine phosphokinase (CPK) and lactate dehydrogenase (LDH) Fractionate bilirubin, if total bilirubin $> 2 \times$ ULN Obtain complete blood count with differential to assess eosinophilia Record the appearance or worsening of clinical symptoms of liver injury, or hypersensitivity, on the adverse event (AE) report form Record use of concomitant medications (including acetaminophen, herbal remedies, and other over-the-counter medications) on the concomitant medications eCRF Record alcohol use on the liver event alcohol intake eCRF Anti-nuclear antibody, anti-smooth muscle antibody, Type 1 anti-liver kidney microsomal antibodies, and quantitative total immunoglobulin G (IgG) or gamma globulins Serum acetaminophen assay Liver imaging (ultrasound, magnetic resonance, or computerized tomography) and/or liver biopsy to evaluate liver disease

[figure not shown]

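### Protocol Section 7.1.2 makes a stop for the Appendix 6 liver chemistry criteria permanent, while Appendix 6 Table 6 treats it as an interruption with possible restart

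*Protocol*

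**What the plan says.** Section 7.1.2 is a single unconditional rule: "A subject must permanently discontinue IP if the subject meets the liver chemistry criteria that are specified in Appendix 6". It names no table, exception or restart path. Section 7.1 points the same way: "Mandatory criteria for permanent discontinuation of IP are documented in Appendix 6". Section 7.1 adds that a drug-induced liver disorder also requires a permanent stop.

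Appendix 6 (Section 10.6) uses different language. The title of Table 6 is "Liver Chemistry Criteria Requiring Investigational Product Interruption and Additional Monitoring", and Table 5 refers forward to it with the words "If at any time the subject meets liver chemistry interruption criteria". The Table 6 actions stop IP immediately and then say: "Do not restart/rechallenge subject with IP unless Medical Monitor approval is granted". The stop becomes permanent at the next step: "If restart/rechallenge not granted, permanently discontinue IP and continue subject in the study for any protocol specified follow up assessments".

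The text above Table 6 sets conditions for re-challenge after an adverse event of interest. The Hepatology Assessment Committee (HAC) must have judged the case unlikely or not related to IP, and enzymes must be back at baseline. A monitoring schedule follows. If enzymes rise above 2 × ULN on re-challenge, "the IP should be discontinued permanently". Section 10.3.3 likewise describes Table 6 stops as either temporary or permanent.

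**The concern.** A rule that every subject who meets the criteria is permanently off drug cannot stand beside a procedure for putting some of them back on it. No text in the public documents says which one prevails.

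Liver injury is the potential risk named in Section 2.3.1, which reports two Hy's Law cases in the programme. The first stop is not in doubt, and no site can restart on its own. The doubt is whether a restart may be approved at all. A site that reads Section 7.1.2 and a site that reads Appendix 6 can reach opposite answers on re-dosing, and each can cite the protocol. Section 8 does not allow waivers, so approving a restart breaches Section 7.1.2.

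Whether a stop counts as permanent also decides three procedural steps: the Early Discontinuation of IP visit (Section 4.1.1), dispensing at later visits (Schedule of Activities) and the Week 20 Follow-up visit (Sections 4.1.1 and 7.1).

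**Working it through.** The plan gives no figure to reproduce here. The check is a comparison of texts.

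**Step 1. What each text does when a Table 6 criterion is first met.**

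| Table 6 criterion | Section 7.1.2 | Appendix 6 |
|---|---|---|
| ALT or AST ≥ 5 × ULN, single value | permanent stop | immediate stop, restart possible |
| ALT or AST ≥ 3 × ULN for ≥ 4 weeks | permanent stop | immediate stop, restart possible |
| ALT or AST ≥ 3 × ULN with bilirubin > 2 × ULN | permanent stop | immediate stop, restart possible |
| ALT or AST ≥ 3 × ULN with INR > 1.5 | permanent stop | immediate stop, restart possible |
| ALT or AST ≥ 3 × ULN, weekly monitoring not possible | permanent stop | immediate stop, restart possible |
| ALT or AST ≥ 3 × ULN with symptoms | permanent stop | immediate stop, restart possible |

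Permanent when first met: 6 of 6 against 0 of 6. Only Table 6 says the stop is immediate. A mandatory permanent stop on meeting a criterion also ends dosing, so the two texts agree on stopping and differ on re-dosing.

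**Step 2. Can the texts be harmonised?**

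- *Section 7.1.2 means only the permanent-stop triggers inside Appendix 6.* There are two: restart refused, and enzymes above 2 × ULN on re-challenge. Section 7.1.2 instead uses the term found in the titles of Tables 5 and 6. Refusal of restart is a decision, not a chemistry criterion. This reading would leave Section 7.1.2 covering only subjects already restarted, which it does not say.
- *Section 7.1.2 is read literally, with no table named.* It then also covers Table 5, where continuing IP is an option, so the conflict is wider and includes the first stop. Limiting the point to Table 6 is the narrower claim.
- *The rule in Section 7.1 on drug-induced liver disorder settles it.* That rule is compatible with re-challenge of cases judged unlikely or not related. It does not tell the reader whether Section 7.1.2 bars re-dosing in those cases.

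**Step 3. Where the texts collide.** For an adverse event of interest, they collide once the HAC has judged the case unlikely or not related, enzymes are at baseline and the Medical Monitor approves. Section 10.3.3 excludes events where the subject cannot be monitored from adverse events of interest. The HAC condition, as worded, therefore does not cover that row, and only Medical Monitor approval stands before a restart.

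**Step 4. Consequences for one subject.** Assumed timing, for illustration only: criterion met at Week 4, restart approved by Week 8. IP is dispensed at Weeks 0, 4, 8 and 12, so 2 dispensing visits remain after Week 4.

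| Step | Section 7.1.2 | Appendix 6 with restart |
|---|---|---|
| Later dosing | none | resumes |
| Early Discontinuation of IP visit | due at the stop | not due, stop not permanent |
| IP at Weeks 8 and 12 | 0 of 2 | 2 of 2 |
| Week 20 visit | waived if the subject stays through Week 16, as the stop precedes Week 12 | due if on IP through Week 16 |

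All 4 steps differ. They are not independent, since all follow from the one label. The illustration does not fit the ≥ 4 weeks criterion: the first post-dose chemistry is at Week 1, and 4 − 1 = 3 weeks of post-dose data at Week 4. It applies to the other five.

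**The case against.** The strongest reply is that the collision is narrow and guarded. For a drug-induced case, Sections 7.1 and 7.1.2 and Appendix 6 all end in no re-dosing. For adverse events of interest, a restart needs a favourable HAC assessment, enzymes at baseline and Medical Monitor approval. The question therefore reaches a sponsor-side decision-maker before any dose is given. A site that follows Section 7.1.2 gives no further dose, so that reading adds no exposure. The counts of six criteria and four steps both come from one difference in wording.

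Most of this stands as a limit on frequency. It does not remove the contradiction: in the cases that pass every gate, one text bars the next dose and the other permits it. The approval step does not help, because the open question is whether approval may be given.

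Two further points are fair. The amendment history lists a Section 6.3.4 on an unblinded Sponsor Medical Monitor. Its current text is not in the public version and might bear on this. SAP Section 3.3 says the last subject completed in August 2020, so an amendment can no longer change how any subject in this trial is handled.

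**Conclusion.** The concern holds. Section 7.1.2 and Appendix 6 give contradictory instructions on re-dosing after a Table 6 liver chemistry criterion is met, for all six criteria. The pointer in Section 7.1 is not itself wrong, because Appendix 6 does contain two permanent-stop triggers, but it does not say that those are the ones meant.

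The number of subjects affected cannot be quantified, because neither document gives an event rate for the Table 6 criteria. The primary analysis and the power calculation do not use the label. The count of adverse events of interest is unaffected because Section 10.3.3 includes both temporary and permanent stops.

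The conclusion rests on the visible text only. The contradiction needs to be fixed because it concerns re-dosing after a signal of the trial's named safety risk.

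**What to change.** Reconcile Section 7.1.2 with Appendix 6 so that each Table 6 criterion leads to one stated action, and have Section 7.1 name the permanent-stop triggers it means. Which rule applies is a clinical choice for the sponsor's safety team, and none is proposed here.

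State when a Table 6 stop counts as permanent for the Early Discontinuation of IP visit (Section 4.1.1), the dispensing note in the Schedule of Activities and the Week 20 waiver (Section 7.1). The dispensing note needs particular care. It cites Section 7.1 but does not limit itself to permanent stops, so read literally it also blocks dispensing after an approved restart.

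The cost is wording in one protocol amendment: Sections 7.1 and 7.1.2, Appendix 6 and one Schedule of Activities note, with no added procedures or patients. As subject participation has ended, the clinical study report should state which rule was applied in practice.
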